**Principal Investigator: [name]**

**date :** **YTD**

## **I. Summary of the Research Plan**

Diabetic kidney disease (DKD), one of the most significant microvascular complications of diabetes, has become the leading cause of end-stage renal disease. Glycemic variability (GV) is considered closely associated with disease progression in these patients. Recent studies indicate that gut microbiota and their serum metabolites play crucial roles in regulating glycemic variability and disease prognosis. However, the mechanisms by which gut microbiota and their metabolites influence glycemic variability and subsequently affect disease outcomes in DKD patients remain unclear. This study aims to address three key questions: ① Characterizing gut microbiota and serum metabolites in DKD patients with varying disease stages and progression levels, while precisely evaluating the prognostic value of gut microbial markers for adverse outcomes. ② Investigating the relationship between gut microbiota, serum metabolites, and glycemic variability in DKD patients. ③ Determining whether gut microbiota and serum metabolites interfere with glycemic variability to influence disease prognosis. To address these questions, this observational prospective cohort study will enroll 270 patients with diabetic kidney disease. By integrating continuous glucose monitoring (CGM), 16S rRNA high-throughput sequencing, and serum non-targeted liquid chromatography-mass spectrometry (LC-MS), this study evaluated glycemic variability, analyzed gut microbiota and serum metabolites, and constructed and validated predictive models for poor prognosis in diabetic kidney disease (DKD) patients. The findings revealed correlations between gut microbiota, serum metabolites, and glycemic variability, elucidated their prognostic roles in DKD, and provided early identification tools for high-risk DKD patients. We aim to offer novel perspectives and strategies for DKD prognosis management, thereby improving clinical outcomes and quality of life for patients.

## **2. Preface**

### **2.1 Research Background and Project Justification**

#### **2.1.1 Epidemiology and Characteristics of Diabetic Nephropathy**

The latest Global Diabetes Atlas, released by the International Diabetes Federation (IDF) in its 10th edition, reveals that approximately 537 million adults worldwide suffered from diabetes mellitus(DM) in 2021. Projections indicate this number will reach 643 million by 2030 and rise to 783 million by 2045 . Diabetic Kidney Disease(DKD), one of the most significant microvascular complications of diabetes, involves chronic kidney damage caused by hyperglycemia. The condition affects the glomeruli, renal tubules, interstitial tissue, and blood vessels, clinically manifesting as persistent albuminuria and/or progressive decline in estimated glomerular filtration rate(eGFR), which may eventually progress to end-stage renal disease(ESRD) . Globally, DKD has become the leading cause of ESRD . The pathophysiological mechanisms of DKD remain complex, with current understanding still requiring further investigation.

The occurrence and development of the disease are related to metabolic disorders, hemodynamic changes and their interaction.

In recent years, an increasing number of studies have shown that DKD is also an inflammatory reactive disease, in which inflammatory pathways play an important role and may be a key factor leading to the progressive damage of organs. In a hyperglycemic environment, inflammatory cell signaling pathways should be activated, mainly including P38 mitogen-activated protein kinase (MAPK), c-Jun N-terminal kinase (JNK), etc., which in turn activate the NF-κB-related signaling pathway. After activation, NF-κB stimulates the transcription of chemokines, adhesion factors, and pro-inflammatory cytokines, leading to inflammatory cell infiltration in renal tissue and promoting the occurrence and development of DKD [4]. In China, DKD has become the primary cause of end-stage renal disease in middle-aged and elderly patients [5]. Therefore, how to prioritize the prevention, identification, and management of DKD is particularly important. Although renal biopsy is the gold standard for diagnosing DKD, it has not been widely adopted due to its invasive and traumatic nature. Current diagnostic criteria for diabetic kidney disease(DKD) primarily rely on clinical manifestations, including the urine protein-to-creatinine ratio, estimated glomerular filtration rate(eGFR), serum creatinine levels, renal ultrasound findings, and retinopathy presence [6]. However, these indicators demonstrate limited diagnostic sensitivity and specificity for DKD, and fail to effectively assess the severity of renal impairment [7]. **Identifying novel biomarkers to identify high-risk populations with progressive DKD for early intervention could improve patient outcomes, establish dynamic and precise disease progression prediction models, and ultimately enable personalized treatment strategies.**

Reducing the incidence of hypoglycemia and minimizing blood glucose fluctuations are crucial for improving the prognosis of diabetic kidney disease (DKD) patients. Timely and accurate blood glucose monitoring is essential for maintaining good glycemic control. However, self-monitoring of blood glucose (SMBG) faces limitations such as poor adherence and constraints from environmental and time factors. Continuous glucose monitoring systems (CGMS) provide diabetic patients with multiple reliable glucose assessment metrics. These include time in range (TIR) and its derivatives time above range (TAR) and time below range (TBR) for evaluating target-range compliance, daily glucose fluctuations measured by standard deviation (SD), coefficient of variability (CV), and mean amplitude of glycemic excursions (MAGE), as well as daily mean absolute differences (MODD) to monitor intra-day variability. Additionally, the system assesses hyperglycemic index (HBGI) and hypoglycemic index (LBGI) to identify risks of hyperglycemia and hypoglycemia [18]. In 2019, the Advanced Technology and Therapy for Diabetes Committee (ATT) emphasized in the "International Expert Consensus on Clinical Application of Continuous Glucose Monitoring" that the core monitoring indicator TIR combined with different blood glucose monitoring indicators can serve as a baseline for evaluating glycemic control. In the 2020 China guidelines for the prevention and treatment of type 2 diabetes, TIR was also included in the control targets [19]. Beck et al. [20] used SMBG data from patients in the Diabetes Control and Complications Trial (DCCT) to calculate TIR and found that TIR was independently associated with the progression of diabetic retinopathy (DR) and proteinuria, suggesting that TIR could serve as an effective end-point indicator in clinical trials. Lu et al. evaluated the relationship between HbA 1C estimated from CGM mean glucose and TIR in 2,893 patients with type 2 diabetes, observing a good linear relationship between the two( $r=-0.91$ ,  $P<0.001$ ). This parameter is more reliable than HbA1c data and can be applied to patients with advanced chronic kidney disease (CKD), including those undergoing dialysis. **Currently, few studies have analyzed the relationship between CGM-derived indicators and the risk of adverse renal outcomes in patients with diabetic kidney disease (DKD).**

### 2.1.3 Metabolism of Intestinal Bacteria and Diabetic Nephropathy

In recent years, there has been growing attention to the role of gut microbiota composition and function in regulating human metabolic processes. The intestinal microbial community participates in key metabolic processes such as food digestion, energy absorption, and glucose metabolism. Disruption of gut microbiota is associated with the occurrence and progression of various common metabolic diseases, including type 1 diabetes mellitus (T1DM) [22], type 2 diabetes mellitus (T2DM) [23], diabetic kidney disease (DKD) [24], and chronic kidney disease (CKD)/end-stage renal disease (ESKD) [25]. In patients with DKD, the gut microbiota typically shows increased pathogenic bacteria and reduced beneficial bacteria [26]. Compared with healthy individuals and diabetic patients without kidney disease (DM), patients with diabetic kidney disease (DKD) exhibit reduced Firmicutes and Prevotella\_9, along with increased Proteobacteria and Escherichia-Shigella. Notably, Prevotella\_9 and Escherichia-Shigella serve as effective biomarkers to distinguish diabetic nephropathy (DN) from DM [27]. A meta-analysis incorporating 15 studies involving 1,640 participants from DKD, DM, non-DKD, and healthy populations revealed characteristic gut microbiota alterations in DKD patients, including increased Hungatella and Escherichia species alongside decreased butyrate-producing bacteria [28]. These findings demonstrate that DKD induces distinctive changes in the gut microbiota profile.

The imbalance of gut microbiota in diabetic kidney disease (DKD) is significantly associated with clinical indicators such as lipid metabolism, glucose metabolism, and renal function. Gut microbiota may serve as a predictive factor for the onset and progression of DKD, potentially playing a crucial role in its pathogenesis. This includes abnormal gut microbiota metabolites, damage to the intestinal mucosal barrier, increased inflammation, activation of the immune system, and activation of the renin-angiotensin system (RAS) [29]. Gut microbiota-derived uremic toxins can induce the secretion of cytokines and chemokines, increase white blood cell recruitment, promote oxidative stress and inflammation, leading to glomerular and tubular damage and fibrosis, thereby accelerating the development and progression of DKD [30]. Short-chain fatty acids (SCFAs), the final metabolites produced by gut microbiota fermentation of dietary polysaccharides, also play significant roles in multiple aspects of renal physiology. These include regulating hormone secretion and metabolism, lowering blood pressure, participating in immune modulation, reducing inflammation and fibrosis, protecting the intestinal epithelial barrier, and inhibiting endotoxemia [31]. Bile acids are synthesized in the liver and metabolized by gut microbiota into secondary bile acids. These secondary bile acids antagonize Farnesoid X receptors (FXR) and Takeda G protein-coupled receptors 5 (TGR5) in the gut, which are involved in diabetic kidney disease (DKD) [32]. Regarding the intestinal mucosal barrier and inflammation, dysbiosis of gut microbiota leads to an increase in Gram-negative (G-) bacteria. Lipopolysaccharide (LPS), the primary structural component of G-bacteria's outer membrane, can disrupt the intestinal mucosal barrier and leak into the bloodstream. This results in elevated serum LPS levels, promotes secretion of inflammatory cytokines, and causes persistent low-level chronic inflammation along with metabolic endotoxemia. Inflammation plays a critical role in the progression of DKD. **Epidemiological and**

**Mechanistic studies have provided strong evidence linking gut microbiota alterations to the development of diabetic kidney disease (DKD). However, the specific gut microbiota and metabolite profiles in patients with DKD at different stages and disease progression levels remain to be elucidated. Notably, the gut microbiota and its metabolites hold significant diagnostic potential for DKD, offering novel perspectives for early disease identification through biomarker applications. Therefore, utilizing these microbial components as biomarkers not only aids in early disease detection but also provides a theoretical foundation for developing innovative therapeutic strategies and intervention approaches.**

#### **2.1.4 Hypothesis and Significance of the Research**

To date, no studies have explored the impact of gut microbiota on the prognosis of diabetic kidney disease (DKD) patients with varying degrees of glycemic variability. Based on existing literature, we propose the following hypotheses: 1) Glycemic variability and specific gut microbiota serum metabolites serve as predictors of adverse cardiovascular events in DKD patients; 2) The gut microbiota and serum metabolites of DKD patients are associated with glycemic variability (GV), which may influence patient outcomes through gut microbiota metabolism. Our proposed methodology includes: 1) Assessing glycemic variability in DKD patients via continuous glucose monitoring (CGM) to investigate its relationship with prognosis and determine optimal glycemic variability control targets. 2) Utilizing 16S rRNA high-throughput sequencing and serum non-targeted liquid chromatography-mass spectrometry (LC-MS) to analyze the relationship between gut microbiota, metabolites, inflammatory factors, and DKD patient prognosis. This study aims to optimize clinical management strategies, establish risk prediction models, promote interdisciplinary research, and improve patient quality of life. The findings will provide new scientific evidence and tools for precision treatment and prognosis management in DKD patients, demonstrating significant scientific and clinical value.

### **2.2 Benefit / Risk Assessment of the Study**

#### **2.2.1. Benefits received**

**① Optimization of glycemic management:** By evaluating glycemic variability with continuous glucose monitoring (CGM), subjects can obtain more accurate glycemic control data, which helps optimize glycemic management, reduce glycemic fluctuations, and reduce the risk of diabetes complications.

**② Personalized treatment:** The findings may reveal the relationship between specific gut bacterial metabolites and prognosis, and provide personalized treatment advice for subjects, such as diet adjustment, probiotics or prebiotics.

**③ Early warning:** If studies find that specific gut bacterial metabolic biomarkers are associated with poor prognosis, subjects could be intervened earlier to prevent cardiovascular events and progression of nephropathy.

#### **2.2.2 Risk profile**

##### **2.2.2.1 Known Adverse Effects:**

**① Wear continuous glucose monitoring (CGM):** Wearing a CGM device may cause mild stinging or itching of the skin.

**② Blood sample collection:** There may be mild pain during blood collection, and there may be mild bruising or swelling at the site of blood collection.

### **2.2.2.2 Potential risks:**

**① Infection risk:** Any invasive procedure (CGM wearing and blood collection) has a minimal risk of infection. The research team will strictly follow aseptic procedures to minimize this risk.

**② Privacy risk:** The study requires the provision of personal health information, and there is a risk of privacy leakage. The research team will take strict confidentiality measures to ensure the security of the personal information of the subjects.

#### **2.2.3 comprehensive evaluation**

**The benefits outweigh the risks:** While there may be some minor discomfort and potential risks involved, participants will receive more precise blood sugar management advice and personalized treatment plans through their research participation, while contributing to public health. The research team will take all necessary measures to ensure participant safety and privacy, guaranteeing that the benefits outweigh the risks.

## **III. RESEARCH OBJECTIVES**

**3.1 Main objective:** To explore the relationship between glycemic variability, gut microbiota metabolites and prognosis of patients with DKD.

**(1) Study subjects:** patients with diabetic nephropathy.

**(2) Exposed factors:** glycemic variability (assessed by continuous glucose monitoring CGM); gut microbiota, serum metabolites (assessed by 16S rRNA high-throughput sequencing technology and serum non-targeted liquid chromatography-mass spectrometry LC-MS) and inflammatory factors.

**(3) Study endpoint:**

**① Primary end point:** progression of DKD. Progression of DKD was defined as renal failure (requiring transplantation or dialysis, or persistent eGFR <15 ml/min/1.73 m^2) or a persistent decline of 30% in eGFR from baseline.

**② Secondary End Points:** I. Cardiogenic Death: Death caused by cardiac disease or related complications. II. Major Adverse Cardiovascular Events (MACE): Including myocardial infarction, stroke, unstable angina pectoris, and other significant cardiovascular events. III. Kidney Transplantation: Successful cases of kidney transplantation surgery. IV. Hypoglycemic Events: Documentation of the frequency and severity of hypoglycemia occurrences.

**(4) Specific objectives:** I. Evaluate the relationship between GV and prognosis in patients with DKD and determine the optimal GV control target. II. Screen for biomarkers of gut microbiota, metabolites, and inflammatory factors associated with DKD prognosis.

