#### 4.1.1 Assessing the impact of glycemic variability on prognosis in patients with diabetic kidney disease

- (1) in prospective cohort studies, patients with DKD were enrolled, and their blood glucose was monitored with a continuous glucose monitor for 14 days, followed by longitudinal follow @-@ up to record adverse prognostic events.
- (2) The relationship between glycemic variability and prognosis was analyzed, and the optimal TIR control target for DKD patients was discussed.

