### 4.2 Innovativeness

(1) Multidimensional assessment: On one hand, continuous glucose monitoring (CGM) technology is employed to dynamically track glycemic variability in diabetic kidney disease (DKD) patients, capturing detailed fluctuations in blood glucose levels. On the other hand, integrated analysis combines 16S rRNA high-throughput sequencing with serum non-targeted LC-MS to comprehensively evaluate gut microbiota composition and serum metabolite profiles, thereby elucidating their correlations with glycemic variability and disease prognosis.

(2) DESIGN OF PROSPECTIVE COHORT STUDY: A prospective cohort study was designed to enroll patients with different clinical stages of DKD and follow up for 3 years. Adverse prognostic events during follow-up were recorded in detail to ensure the continuity and integrity of the collected data, which provided a strong guarantee for the accuracy and reliability of the study results.

(3) multilevel data integration: the multilevel data, including glycemic variability, clinical indicators, gut microbiota, serum metabolites and inflammatory factors, were integrated to construct a predictive model for DKD prediction.

The risk of adverse prognostic events provides a more comprehensive and accurate tool for clinical risk assessment.

[figure not shown]

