#### 1) Inclusion Criteria:

- ① Age 18-65 years;
- ② The diagnosis of DKD meets the relevant criteria in the "China Diabetes Nephropathy Prevention and Treatment Guidelines (2021 Edition)";
- ③ Type 2 diabetes mellitus, treated with insulin analogues or oral antidiabetic drugs, diagnosed according to the 1999 WHO criteria;
- ④ no changes in the antidiabetic regimen were made for at least 3 months before enrollment.
- ⑤ informed consent was obtained voluntarily.

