## **2) Exclusion criteria:**

- ① The patients with diabetes mellitus complicated with ketoacidosis, primary glomerulonephritis, nephrotic syndrome, lupus nephritis and other primary or secondary kidney diseases.
- ② The body was in a state of stress such as infection and trauma.
- ③ women who are pregnant, breastfeeding, or planning to become pregnant next month;
- ④ severe skin lesions, such as extensive eczema, extensive scarring, extensive tattoos, papular dermatitis, severe edema and psoriasis;
- ⑤ Sensory surface of the sensor is scarred due to severe skin burns, scalds, sunburns, trauma, ulcers, surgery, etc.
- ⑥ coagulation dysfunction, anemia or abnormal hematocrit;
- ⑦ Patients with chronic gastrointestinal diseases or a history of biliary or gastrointestinal surgery were excluded from the study.
- ⑧ consumed probiotics, prebiotics, or received antibiotic treatment for more than 3 days in the past 3 months; consumed yogurt or yogurt-containing foods or beverages in the past week.

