### (3) Follow-up in the Queue:

- 1) follow-up time: 3 years after discharge.
- 2) Follow-up methods: outpatient follow-up, telephone follow-up and review of relevant medical records.
- 3) Outcome measures:

**① Primary end point:** progression of DKD. Progression of DKD was defined as renal failure (requiring transplantation or dialysis, or persistent eGFR <15 ml/min/1.73 m^2) or a persistent decline of 30% in eGFR from baseline.

**② Secondary End Points:** I. Cardiogenic Death: Death caused by cardiac disease or related complications. II. Major Adverse Cardiovascular Events (MACE): Including major cardiovascular events such as myocardial infarction, stroke, and unstable angina. III. Kidney Transplantation: Successful cases of kidney transplantation surgery. IV. Hypoglycemic Events: Record the frequency and severity of hypoglycemia occurrences.

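### The renal-failure part of the primary endpoint is not tied to baseline, so a patient already in renal failure at entry could be counted as progression

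*Protocol*

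**What the plan says.** The primary endpoint appears in Protocol 3.1 (3) and again, in the same terms, in 5.5 (3). It has two limbs. The first is renal failure: "Progression of DKD was defined as renal failure (requiring transplantation or dialysis, or persistent eGFR <15" ml/min/1.73 m². The second is "or a persistent decline of 30% in eGFR from baseline". The reference to baseline belongs to the second limb only.

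On who may enter, 5.3.2 relies on a guideline diagnosis ("The diagnosis of DKD meets the relevant criteria in the" 2021 national guideline). Its kidney-related exclusions concern other kidney diseases and nephrotic syndrome. An indirect filter is "coagulation dysfunction, anemia or abnormal hematocrit". No eGFR floor, dialysis exclusion or transplant exclusion is written. Section 4.2 intends to "enroll patients with different clinical stages of DKD and follow up for 3 years", with no upper stage named.

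On how the endpoint is used, 5.4 splits patients into two groups by adverse prognosis and asks for at least 30 in each. Section 5.8.2 compares favorable with unfavorable prognosis groups by MaAsLin, PERMANOVA and OPLS-DA, and also lists Cox regression for time-to-event data.

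**The concern.** A patient whose eGFR is persistently below 15 at entry, or who is already on dialysis, satisfies the first limb as written at the first follow-up visit without any change in condition. The text does not say how to classify such a patient, so two assessors could disagree.

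This matters most in the two-group marker comparisons. A Cox model at least prompts the analyst to ask who is at risk at time zero; a comparison of patients grouped by final status does not. The protocol's own background (2.1.2 and 2.1.3) links kidney failure and hemodialysis to altered gut flora and disturbed glucose metabolism. A patient with prevalent renal failure in the adverse group would therefore contribute the profile of existing kidney failure. A marker of low kidney function could be reported as a marker of progression. With only 30 events planned, a few such patients carry weight.

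**Working it through.** **The plan's own figure.** From 5.4: 975/156 × 30 = 187.5. Adding 10% gives 187.5 × 1.10 = 206.25; dividing by 0.90 gives 208.3. Both are close to the 210 enrolled, and 210 + 60 = 270. The sample-size arithmetic reproduces and is not at issue.

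**Inputs.**
- Event rate r: 156/975 = 0.160 over a mean of 4.7 years (5.4). Rescaled to the 3-year follow-up at constant hazard (an assumption): 1 − (1 − 0.16)^(3/4.7) = 0.1053.
- Modeling cohort: 210 (5.4).
- Share p already in renal failure at entry: not in the protocol. Assumed 1%, 2%, 5% and 10%.

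**Share of counted events that are prevalent**, if every prevalent case is counted and the others have events at rate r: p / [p + (1 − p) r]. For p = 0.05:
- r = 0.160: 0.05 / (0.05 + 0.95 × 0.160) = 0.05/0.202 = 0.248
- r = 0.1053: 0.05 / (0.05 + 0.95 × 0.1053) = 0.05/0.150 = 0.333

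| Assumed p | Patients of 210 | Share of counted events, r = 0.160 | Share, r = 0.1053 | New events among 30 counted |
|---|---|---|---|---|
| 1% | about 2 | 6% | 9% | 28 or 27 |
| 2% | about 4 | 11% | 16% | 27 or 25 |
| 5% | 10-11 | 25% | 33% | 23 or 20 |
| 10% | 21 | 41% | 51% | 18 or 15 |

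The last column is 30 × (1 − share), at the two rates in turn.

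**Effect on a marker with no prognostic value.** Simulation with 210 patients and 6,000 runs per cell. The marker is higher only in patients with prevalent renal failure, and all of them are coded as events. Tests are Welch's t-test and linear regression adjusted for the four covariates named in 5.8.2. The liability to prevalent renal failure is correlated 0.3 (assumed) with two of those covariates. Entries are the proportion of studies declaring a difference at nominal 5%, as a range over both rates and both tests.

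| Marker shift | p = 1% | 2% | 5% | 10% |
|---|---|---|---|---|
| 0.25 SD | 5% | 5%-6% | 6%-8% | 10%-12% |
| 0.5 SD | 6% | 6%-7% | 12%-14% | 22%-29% |
| 1 SD | 6%-8% | 9%-13% | 27%-37% | 63%-75% |

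With prevalent cases left out (Welch test only), every cell returns to 5%-6%. Adjusting for age, sex, disease duration and baseline glucose does not remove the effect, because none of them measures kidney function. Propensity score matching, which 5.8.2 also plans, was not simulated.

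**The case against.** The best counter-argument is that the protocol, read as a whole, means new events. The endpoint is named progression and is repeated under the follow-up heading. Section 4.1.1 follows patients "to record adverse prognostic events", and the schedule in 5.6 places progression events at Visits 4 to 6. This stands as evidence of intent. A reader might infer that the protocol directs prevalent cases to be counted; it does not. The supportable statement is that they could be counted.

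A reader might also infer that dialysis patients are to be enrolled, because 2.1.2 says a CGM measure "can be applied to patients with advanced chronic kidney disease (CKD), including those undergoing dialysis". That sentence is literature background, not eligibility. Section 4.2 does not say that the last stage is included, and the cited guideline is not at hand. Recruitment is from an endocrinology ward, and the exclusions for anemia or abnormal hematocrit, nephrotic syndrome and severe edema probably remove some late-stage patients. So the number affected may be small. These filters act only incidentally, though, and none sets a renal-function limit.

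It can be said that handling patients who meet an endpoint at baseline belongs in an analysis plan, which is not shown. That would be persuasive if the protocol had left the endpoint open. It fixes the definition twice, in wording that admits prevalent cases.

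The covariate list in 5.8.2 is given as examples, so baseline eGFR is not ruled out. Finally, it is tempting to leave out everyone with baseline eGFR below 15 on the ground that no new event would be lost. That does not follow: such a patient can still start dialysis, need a transplant or have a persistent 30% decline.

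**Conclusion.** The point holds as an ambiguity in the primary endpoint that can lead to a wrong result and should be fixed; confidence is medium. The text supports three statements: only the decline limb is tied to baseline, eligibility states no renal-function, dialysis or transplant limit, and the two-group comparisons have no built-in protection against prevalent cases.

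The size is uncertain because prevalence at entry, marker shift and covariate correlation are all assumed, and the calculation counts every prevalent case as an event. On those assumptions the effect is small at 1%-2% prevalence. It is material from about 5%, and only for markers shifted by 0.5 SD or more. Nothing in the protocol shows that prevalence reaches 5%.

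The point concerns the renal-progression endpoint only. A reader might extend it to the prediction model, but 3.2.1 gives that model all-cause death as its primary endpoint and MACE as secondary, and prevalent renal failure does not satisfy either.

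**What to change.** 1. State in 3.1 (3), 5.5 (3) and 5.8.2 that a renal-failure component counts as progression only if it was not present at baseline.
2. For the renal-progression endpoint and the renal-prognosis group comparisons, place patients already on dialysis or with a kidney transplant at entry outside the at-risk set.
3. For patients with baseline eGFR below 15 (the protocol's own threshold) who are not on dialysis, do not count the eGFR component. In the main analysis, either count only a new dialysis start, a transplant or a persistent 30% decline, or leave these patients out. Report the other choice as a sensitivity analysis.
4. Classify baseline status from the scheduled renal test and any earlier values on record, since one test cannot show persistence. Record review is already a study method ("outpatient follow-up, telephone follow-up and review of relevant medical records").
5. Add baseline eGFR, available from the kidney-function test already planned, to the covariates in 5.8.2 for the renal prognostic models.
6. Leave the all-cause-death and MACE outcomes in 3.2.1, and the cross-sectional glycemic-variability, microbiota and metabolite analyses, unrestricted.
7. Report the number of patients affected.

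Whether such patients should be enrolled is for the investigators to decide.

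**Cost.** If all prevalent cases were left out, the at-risk set would fall from 210 to about 208, 206, 200 or 189 at 1%, 2%, 5% or 10% prevalence. Events among the remaining patients, 210 × (1 − p) × r, would be about 33, 33, 32 and 30 at the 16% rate, or 22, 22, 21 and 20 at 10.5%. With 10% dropout (189 in place of 210) they would be 30, 30, 29 and 27, or 20, 20, 19 and 18. These counts credit no new events to the patients left out, so a few could be lost if those with baseline eGFR below 15 are removed. The remaining cost is three wording changes, the record check, one degree of freedom for eGFR and one sensitivity analysis.

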## 5.4 Methods for Determining the Required Sample Size for Research

This exploratory study investigates the impact of gut microbiota and related metabolites on prognosis in diabetic kidney disease (DKD) patients. To achieve this, patients will be divided into two groups based on adverse prognosis outcomes, with subsequent comparisons of gut microbiota and metabolite differences between groups. To minimize microbial variations caused by individual differences, each group requires at least 30 participants, meaning there must be at least 30 patients with adverse prognosis events. Drawing from existing research, a 2023 study published in *\*Diabetes Care\** [Diabetes Care.2023;46(4):868-873.] included 975 DKD patients with an average follow-up of 4.7 years, reporting 156 major outcomes of DKD progression. Consequently, the total sample size was calculated as  $975/156*30=187.5$ . Considering potential dropouts and incomplete responses, we typically increase the sample size by 10%, ultimately enrolling 210 patients as the modeling cohort. Additionally, 60 DKD patients were included as a validation cohort. During actual recruitment, sample size adjustments may be made based on factors such as recruitment speed and data quality. Regular assessments of sample adequacy should also be conducted to ensure statistical power.

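### The main objective promises an optimal GV control target, but some 20 to 30 events cannot locate a threshold reliably and no separate data are assigned to confirm one

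*Protocol*

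**What the plan says.** Protocol section 3.1, item (4), sets the objective as "Evaluate the relationship between GV and prognosis in patients with DKD and determine the optimal GV control target". Section 2.1.4 says that CGM will be used "to investigate its relationship with prognosis and determine optimal glycemic variability control targets". Section 4.1.1 names a different quantity and uses a weaker verb: "the optimal TIR control target for DKD patients was discussed".

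Section 5.4 sizes the study for a comparison of microbiota and metabolites between patients with and without an adverse outcome: "each group requires at least 30 participants, meaning there must be at least 30 patients with adverse prognosis events". The event rate comes from a published cohort that "included 975 DKD patients with an average follow-up of 4.7 years, reporting 156 major outcomes of DKD progression". The sum is "975/156*30=187.5", and then "we typically increase the sample size by 10%, ultimately enrolling 210 patients as the modeling cohort". A further 60 patients form a validation cohort, which sections 4.1.4, 5.8.2 and 9 assign to the prediction model. Follow-up is 3 years (section 5.5).

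Section 5.8.2 lists Cox regression with covariate adjustment, among other methods. It gives no method for deriving a target and no significance level. GV groups number two in section 4.1.3 and three in section 5.5(4), with no boundary in either place. Section 9 schedules the grouping from CGM data for January to May 2026, and again before the end of 2027. The association analysis follows in 2028.

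**The concern.** A control target for a continuous index has to be read from the relation between that index and outcome. If it is found by trying cut-offs and keeping the one that separates prognosis best, every candidate is a further test of the same hypothesis. The p-value and hazard ratio at the winning cut-off are then too favourable. If risk changes smoothly with GV, there is no true threshold to find, and the position of the chosen value depends largely on chance.

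At stake is how the result is presented. A value that would not reproduce could be reported as a control target for DKD patients, with no part of the study assigned to check it.

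**Working it through.** **1. The plan's own figure.** 156/975 = 16.0% over a mean of 4.7 years. 30/0.16 = 187.5, as section 5.4 states. A 10% allowance gives 187.5 × 1.10 = 206.25 or 187.5/0.90 = 208.3. Both agree with 210 after rounding up.

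**2. Events over 3 years.** With a constant hazard, λ = −ln(1 − 0.16)/4.7 = 0.0371 per year, and the 3-year risk is 1 − exp(−3 × 0.0371) = 10.5%. Expected events are 187.5 × 0.105 = 19.7, 210 × 0.105 = 22.1, and 60 × 0.105 = 6.3 in the validation cohort. So 30 is the design target, and the cited rate implies about 20 to 22.

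**3. False positives if cut-offs are searched (assumed procedure).** Assumptions: one index unrelated to outcome, censoring at 3 years, largest |z| over the candidate cuts compared with 1.96. Log-rank rows use 5,000 simulated cohorts each. The other rows use 20,000 and a chi-square test on the binary outcome.

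| Candidate cut-offs | 188 patients, 30 events | 210 patients, 30 events | 189 patients, 20 events |
|---|---|---|---|
| Every cut, 5th–95th percentile, log-rank | 48% | 48% | 48% |
| Every cut, 10th–90th, log-rank | 42% | 44% | 41% |
| Every cut, 20th–80th, log-rank | 32% | 32% | 31% |
| Every cut, 25th–75th, log-rank | 29% | 29% | 27% |
| Youden cut, then chi-square | 40% | – | 39% |
| Deciles, chi-square | 25% | – | – |
| Quartiles, chi-square | 16% | – | – |
| Tertiles, chi-square | 10% | – | – |

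For comparison, one cut fixed at the median gives about 5% with the log-rank test. It gives 7.3% with the chi-square test, because counts are discrete, so part of the tertile figure is not due to searching.

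For a full 10th–90th percentile search, the Miller-Siegmund approximation needs |z| of about 3.05 (nominal p about 0.0023) to hold a true 5%.

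**4. Where the chosen cut-off falls (10th–90th search, 30 events, 188 patients; log-linear effect, no true threshold).**

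| True effect per SD | Middle 50% of chosen cut-offs | 95% range |
|---|---|---|
| None | 23rd–77th percentile | 10th–90th (all of it) |
| HR 1.3 | 38th–83rd | 12th–90th |
| HR 1.5 | 49th–85th | 16th–90th |
| HR 2.0 | 65th–87th | 35th–90th |

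With 210 patients and a log hazard ratio of 0.4 per SD (HR about 1.5), the 95% range is the 14th to the 90th percentile.

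**5. Exaggeration at the chosen cut-off (210 patients, 30 events).** With no effect, the median apparent hazard ratio is 2.3, in either direction. With log hazard ratio b = 0.4 per SD, it is 3.3. The true ratio of mean hazards above and below a cut c on the SD scale is [Φ(b − c)/(1 − Φ(c))] / [Φ(c − b)/Φ(c)]. At the median (c = 0) this is 0.655/0.345 = 1.9. At the 90th percentile (c = 1.28) it is (0.189/0.1)/(0.811/0.9) = 2.1.

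**The case against.** The strongest reply is that the protocol never describes such a search. It names no scan of cut-offs, no smallest-p rule, no Youden index, no significance level and no test at a chosen value. A target could be read from a continuous risk curve. The grouping in section 9 uses CGM data and is scheduled before the outcome analysis, so the groups need not be driven by outcome. The method for a cut-off is also commonly left to a SAP, which may exist. Section 5.4 calls the work exploratory, and section 4.1.1 only undertakes to discuss a target.

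Most of this stands. A reader might infer that the plan as written carries a 40% false-positive rate for the GV association, or that the cut-off's location is arbitrary. The document supports neither. The 40% belongs to one assumed procedure. The association can be tested without inflation by keeping GV continuous in the Cox model or by using groups fixed before outcomes are seen. Location is close to arbitrary only with no effect or a weak one.

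The reply does not rescue the objective. Sections 2.1.4 and 3.1 undertake to determine a target, and that wording is in the protocol itself. A SAP could correct a p-value, but it cannot make 20 to 30 events locate a threshold. Nor can a validation cohort with about 6 expected events confirm one.

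**Conclusion.** The point holds as a mismatch between a stated objective and the data available for it. The protocol promises an optimal control target from a cohort sized for a different comparison. That cohort has 30 events by design and about 22 at the cited rate over 3 years, and nothing is reserved for confirmation. The text also differs on whether GV or TIR is the index and on whether there are two GV groups or three.

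The size is conditional. If the target is chosen by searching against outcome and tested uncorrected at two-sided 5%, the false-positive rate with no GV effect runs from about 10% to 48%, depending on the search. At about HR 1.5 per SD the 95% range of the cut-off covers nearly the whole interval searched, and it narrows as the effect grows. These figures assume one index, a constant baseline hazard and no loss to follow-up.

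**What to change.** In sections 2.1.4, 3.1(4) and 4.1.1, replace the aim of determining an optimal target with estimating the GV-outcome relationship on the continuous scale. In section 5.8.2, specify this within the adjusted Cox model: a linear term, a 3-knot restricted cubic spline as a check, and confidence bands. Reconcile whether GV or TIR is the index and how many GV groups there are.

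Any cut-off used for analysis should be fixed before outcomes are seen. Otherwise it should be labelled exploratory, reported with a maximally-selected-statistic (permutation) p-value and a bootstrap interval for its location, and not presented as a control target. No clinical target value is proposed here.

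The cost is protocol wording and a little analysis code, with no new patients or data. What is given up is a single headline cut-off; the study would report a risk curve.
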